### **9.7 Special Situations**

Certain safety events, called 'Special Situations', that occur in association with study drug may require reporting. These Special Situations include, but are not limited to, the following:

- Overdose of the medicinal product
  - Ferric citrate overdose - Accidental ingestion and resulting overdose of iron-containing products is a leading cause of fatal poisoning in children under

6 years of age. In case of accidental overdose, call a physician or poison control center immediately. Advise subjects of the risks to children and to keep ferric citrate out of the reach of children.

An overdose of iron can lead to iron toxicity. Iron toxicity can be classified as corrosive or cellular. Ingested iron can have an extremely corrosive effect on the GI mucosa, which can manifest as nausea, vomiting, abdominal pain, hematemesis, and diarrhea; patients may become hypovolemic because of significant fluid and blood loss. Cellular toxicity occurs with the absorption of excessive quantities of ingested iron. Severe overdose causes impaired oxidative phosphorylation and mitochondrial dysfunction, which can result in acidosis and cellular death. The liver is one of the organs most affected by cellular iron toxicity, but other organs such as the heart, kidneys, lungs, and the hematologic systems may also be impaired. With chronic iron overload, the deposit of iron into visceral organs can cause organ dysfunction due to siderosis [Spanierman 2010].

Acute intoxication is most commonly reported in children ingesting large quantities of ferrous sulfate or chewable vitamins with iron; thus, ferric citrate must be kept out of the reach of children unless administered under a pediatric clinical study protocol.

An overdose of iron in pregnant women may carry a risk for spontaneous abortion, gestational diabetes, and fetal malformation.

Special situations should be collected whether they result in an SAE or not. Special situations with associated SAE should also be reported on the corresponding SAE forms, following applicable SAE process.

## **10.0 STATISTICAL CONSIDERATIONS**

Data collected throughout the study will be summarized using descriptive statistics and listed in by-subject listings. Continuous variables will be summarized using number of subjects with data, mean, standard deviation, median, minimum, and maximum. For categorical variables, the number and percentage of subjects in each category will be tabulated. Summaries will be provided by treatment group within appropriate analysis populations and by time point/time period, as appropriate.

### **10.1 Sample Size Determination**

The sample size for this study is driven by the primary endpoint, initiation of maintenance dialysis or all-cause mortality and is based on the observed data from the pilot study using nearly identical inclusion and exclusion criteria. The observed rate of the primary composite endpoint in the pilot study (all-cause mortality, maintenance dialysis or kidney transplant) for patients in the standard of care arm was 0.94 events per person-year of follow up. The observed hazard ratio was 0.42 (58% relative risk reduction,  $p=0.002$ ) for the primary composite endpoint when comparing ferric citrate treated patients versus usual care.

Assuming 1 year recruitment and 0.75 years of follow up (9 months) for each individual and a hazard ratio of 0.60 (40% relative risk reduction), a sample size of 400 patients (200 per arm)

provides 90% power with a 2-sided alpha  $p < 0.05$ . Assuming a hazard ratio of 0.50 (50% relative risk reduction), a sample size of 225 patients provides 90% power with a 2-sided alpha  $p < 0.05$ .

## **10.2 Populations for Analyses**

The following analysis populations will be used in this study:

- Randomized population: defined as all randomized subjects.
- Full analysis population: defined as randomized subjects receiving one or more doses of study drug. This population will be analyzed based upon the randomized treatment.
- Safety population: defined as all subjects who received at least one dose of study drug. This population will be analyzed based upon the actual treatment received.
- Per protocol population: defined as all randomized subjects who received study drug and have no protocol deviations affecting the primary endpoint analyses. Protocol deviations leading to exclusion from the PP population will be specified prior to database lock on a blinded basis and recorded in a separate document.

## **10.3 Missing Data**

Discontinuation from study intervention is different from discontinuation from the study, and remaining study procedures will be completed as indicated by the study protocol unless the subject withdraws consent for participation in the study.

All data pertaining to the primary and secondary endpoints collected at any point during the study, both during study drug treatment and post-study drug treatment discontinuation, will be used for the primary analysis of the endpoints and its individual components.

Unless stated otherwise in the Statistical Analysis Plan, missing data for all other endpoints will not be imputed and the analysis will be based on observed data.

## **10.4 Statistical Analyses**

### **10.4.1 General Considerations**

Data summaries for categorical variables such as SAEs will use descriptive statistics including number of subjects, and proportions. Data summaries for continuous variables such as laboratory parameters will use descriptive statistics for mean, standard deviation, median, minimum, and maximum. Within-group changes from baseline for continuous parameters will be assessed.

### **10.4.2 Analysis of Primary Endpoint(s)**

The primary endpoint is the time to composite endpoint of initiation of maintenance dialysis or all-cause mortality. It will be considered as confirmatory evidence of efficacy. The primary endpoint will be analyzed by Cox-proportional hazards regression model. HRs and

corresponding 95% confidence intervals will be presented for the primary endpoint (initiation of maintenance dialysis or all-cause mortality).

#### **10.4.3 Analysis of Secondary Endpoint(s)**

For the below secondary endpoints, Cox-proportional hazard regression model or competing risk analyses will be conducted. HRs and corresponding 95% confidence intervals will be presented.

- Time to first event hospitalization reported as a SAE (excluding disease-related hospitalization [e.g., fistula replacement, dialysis initiation, kidney transplant] and elective procedures),
- Component of Primary – time to initiation of maintenance dialysis
- Component of Primary – time to all-cause mortality

A full description of the analyses performed on secondary endpoints will be provided in the statistical analysis plan. A *pre-specified* process for identifying hospitalization events to be included in the analysis of the hospitalization secondary endpoint will be used.

#### **10.4.4 Tertiary/Exploratory Endpoint(s)**

A full description of the analyses performed on exploratory endpoints will be provided in the statistical analysis plan. Exploratory endpoints include:

- Rate of hospitalizations and rate of hospitalization days prior to initiating maintenance dialysis
- Receipt of kidney transplant prior to initiating maintenance dialysis
- Cumulative dose over time of rescue therapy for anemia including (individually, [ESA, intravenous iron, RBC transfusion]) prior to initiating maintenance dialysis

#### **10.4.5 Safety Analyses**

##### **10.4.5.1 Analysis of Adverse Events**

All analyses of safety data will use the safety population.

SAEs and Adverse Events of Special Interest will be summarized using the number and percentage for all subjects in the safety population.

All SAEs will be coded using Medical Dictionary for Regulatory Activities (MedDRA) classification. Treatment-emergent SAEs will be summarized by system organ class and preferred term (PT) for each treatment group. SAEs will also be summarized by their maximum severity.

Summaries will also be provided for the following types of SAEs:

- Related SAEs (including all categories for relationship to study drug other than “Unrelated”, as determined by the Investigator)

#### **10.4.6 Baseline Descriptive Statistics**

Descriptive statistics will be generated for demographic and pretreatment variables for the randomized population defined in Section 10.2.

Medical history terms will be summarized for each treatment group based on the randomized population.

#### **10.4.7 Planned Interim Analyses**

No formal interim analysis is planned.

#### **10.4.8 Sensitivity Analyses**

Sensitivity analyses will be conducted to explore the robustness of the primary endpoint analysis. Full details of the sensitivity analyses will be described in the statistical analysis plan but may include analyses such as those related to compliance with study drug (per-protocol analysis) or excluding endpoint events occurring within 8 weeks of study start.

#### **10.4.9 Sub-Group Analyses**

Analyses of the primary, secondary, and exploratory endpoints may be performed in subgroups with more details to be included in the final SAP, including:

- eGFR within 3 months of Screening:
  - $\geq 15$  to  $\leq 20$  ml/min/1.73 m^2
  - $< 15$  ml/min/1.73 m^2
- 4-variable Kidney Failure Risk Equation (KFRE) score [Tangri 2011] within 3 months of Screening:
  - $\geq 20\%$
  - $< 20\%$  over 2 years

### **11.0 SUPPORTING DOCUMENTATION AND OPERATIONAL CONSIDERATIONS**

#### **11.1 Ethical Conduct of the Study**

The study will be conducted in accordance with the Declaration of Helsinki on Ethical Principles for Medical Research Involving Human Subjects, adopted by the General Assembly of the World Medical Association (2013).

In addition, the study will be conducted in accordance with the protocol, the International Council for Harmonization (ICH) E6 (R2) guideline on Good Clinical Practice (GCP), and applicable local regulatory requirements and laws.

## **11.2 IRB and Ethics Committees**

It is the responsibility of the investigator to have prospective approval of the study protocol, protocol amendments, informed consent forms, and other relevant documents, (e.g., recruitment advertisements, if applicable) from the IRB/IEC. All correspondence with the IRB/IEC will be retained in the Investigator File. Copies of IRB/IEC approvals will be forwarded to the Investigator-Sponsor/Investigator or its designee.

In case of a substantial protocol amendment, the Investigator-Sponsor/Investigator will obtain approval from responsible Regulatory Authorities before implementation.

The only circumstance in which an amendment may be initiated prior to IRB/IEC approval is where the change is necessary to eliminate apparent immediate hazards to the subjects. In that event, the investigator will notify the IRB/IEC and the Investigator-Sponsor in writing immediately after the implementation.

## **11.3 Informed Consent Process**

The Investigator or designee will explain the nature of the study to the subject and answer all questions regarding this study. Prior to any study-related procedures being performed on the subject, the informed consent form (ICF) will be reviewed, signed, and dated by the subject or their legally acceptable representative, as well as the person who administered the informed consent, and any other signatories, according to local requirements. Informed consent may be obtained using an electronic consent process (e-consent) following all applicable ICH/GCP and IRB guidelines and regulations. A copy of the signed ICF will be given to the subject and the original will be placed in the subject's medical record. An entry must also be made in the subject's dated source documents to confirm that informed consent was obtained prior to any study-related procedures and that the subject received a signed copy.

The signed consent forms will be retained by the Investigator and made available (for review only) to the study monitor, auditor, regulatory authorities and/or IRB/IEC and other applicable individuals upon request.

The ICFs will be in compliance with ICH GCP, local regulatory requirements, and legal requirements. The ICFs used in this study, and any changes made during the course of the study, will be prospectively approved by both the IRB/IEC and the Investigator-Sponsor before use.

## **11.4 Financial Disclosure**

Investigators and sub-investigators will provide the Sponsor-Investigator with sufficient, accurate financial information, as requested, to allow the Sponsor-Investigator to submit complete and accurate financial certification or disclosure statements to the appropriate regulatory authorities. Investigators are responsible for providing information on financial interests, during the course of the study, and for 1 year after completion of the study.

## **11.5 Confidentiality and Data Privacy**

All parties will ensure protection of subject personal data and will not include subject names on any Investigator-Sponsor forms, reports, publications, or in any other disclosures, except where required by law. In case of data transfer, the Investigator-Sponsor will maintain high standards of confidentiality and protection of subject personal data.

The Investigator/Investigator-Sponsor and designees affirm and uphold the principle of the subject's right to protection against invasion of privacy. Throughout this study, a subject's source data will only be linked to the Investigator-Sponsor's clinical study database or documentation via a unique identification number. As permitted by all applicable laws and regulations, limited subject attributes, such as sex, age, or date of birth, and subject initials may be used to verify the subject and accuracy of the subject's unique identification number.

To comply with ICH guidelines for GCP and to verify compliance with this protocol, the Investigator-Sponsor requires the Investigator to permit its monitor or designee's monitor, representatives from any regulatory authority (e.g., FDA), the Investigator-Sponsor's designated auditors, and the appropriate IRBs to review the subject's original medical records (source data or documents), including, but not limited to, laboratory test result reports, electrocardiogram reports, admission and discharge summaries for hospital admissions occurring during a subject's study participation, and autopsy reports. Access to a subject's original medical records requires the specific authorization of the subject as part of the informed consent process.

## **11.6 Data Handling and Record Keeping**

### **11.6.1 Data Collection and Management Responsibilities**

This study will utilize an electronic data capture (EDC) system to manage data collection during this trial that is fully Code of Federal Regulations 21 part 11 compliant. An EDC system contains certain functionality including, but not limited to, a graphical user interface to help facilitate data entry, a data validation element to check user data, and a reporting function. eCRFs available through this system are required and will be completed for each randomized subject.

Any form of data from the electronic system are the sole property of the Investigator-Sponsor and will not be made available in any form to third parties, except for authorized representatives of the Investigator-Sponsor or appropriate regulatory authorities, without written permission from the Investigator-Sponsor.

The Investigator has ultimate responsibility for the accuracy, authenticity, and timely collection and reporting of all clinical, safety, and laboratory data entered in the eCRF or any other data collection forms.

In most cases, the source documents are contained in the subject's chart at the hospital or the physician's office. In these cases, data collected on the eCRFs will match the data in those charts.

### **11.6.2 Study Records Retention**

To enable evaluations and/or audits from regulatory authorities or the Investigator-Sponsor, the Investigator agrees to keep records, including the identity of all participating subjects (sufficient

information to link records (e.g., eCRFs and hospital records)), all original signed ICFs, copies of all eCRFs, SAE forms, source documents, detailed records of drug disposition, and adequate documentation of relevant correspondence (e.g., letters, meeting minutes, and telephone calls reports). The records will be retained by the Investigator according to the ICH, local regulations, or as specified in the Clinical Study Agreement, whichever is longer.

If the Investigator becomes unable, for any reason, to continue to retain study records for the required period (e.g., retirement and relocation), the Investigator-Sponsor will be prospectively notified. The study records will be transferred to a designee acceptable to the Investigator-Sponsor, such as another Investigator, another institution, or to the Investigator-Sponsor. The Investigator will obtain Investigator-Sponsor's written permission before disposing of any records, even if retention requirements have been met.

## **11.7 Reporting of Safety Issues and Serious Breaches of the Protocol or ICH GCP**

In the event of any prohibition or restriction imposed (e.g., clinical hold) by an applicable Competent Authority, or if the Investigator is aware of any new information which might influence the evaluation of the benefits and risks of the investigational product, the Investigator-Sponsor will be informed immediately.

In addition, the Investigator will inform the Investigator-Sponsor immediately of any urgent safety measures taken by the Investigator to protect the study subjects against any immediate hazard, and of any serious breaches of this protocol or of ICH GCP, defined as a breach that will likely affect the safety or physical or mental integrity of subjects or the scientific value of the trial, that comes to the attention of the Investigator.

## **11.8 Study Discontinuation and Closure**

The Investigator-Sponsor reserves the right to discontinue the study prior to inclusion of the intended number of subjects but intends only to exercise this right for valid scientific or administrative reasons. After such a decision, the Investigator will contact all participating subjects, within a time period specified by the Investigator-Sponsor, to inform them of the decision to discontinue the study.

### **11.8.1 Criteria for Premature Termination or Suspension of the Study**

The following criteria may result in either temporary suspension or early termination of the study:

- New information regarding the safety or efficacy of the study drug that indicates a change in the known risk/benefit profile for the compound, such that the risk/benefit is no longer acceptable for subjects participating in the study
- Significant violation of GCP that compromises the ability to achieve the primary study objectives or compromises subject safety
- Request from regulatory agencies

The Investigator-Sponsor reserves the right to discontinue the study for other valid administrative reasons. If the study has been suspended or terminated, prompt notification will

be given to Investigators, IRBs, and regulatory authorities in accordance with regulatory requirements.

### **11.8.2 Criteria for Premature Termination or Suspension of Study Sites**

A study site may be terminated prematurely or suspended if the study site (including the Investigator) is found to be in significant violation of GCP, protocol, contractual agreement, or is unable to ensure adequate performance of the study.

The Investigator will notify the Investigator-Sponsor if the trial is terminated by the Investigator or the IRB at the site. If the Investigator, IRB, or Investigator-Sponsor decides to terminate or suspend the trial conduct at a particular study site for safety, non-enrollment, non-compliance with the protocol, or other unanticipated reasons, the above parties will be promptly notified.

### **11.8.3 Criteria for Premature Termination or Suspension of the Study or Study Sites**

In the event that the Investigator-Sponsor elects to terminate or suspend the study or the participation of an investigational study site, a study-specific procedure for early termination or suspension will be provided by the Investigator-Sponsor; the procedure will be followed by applicable study sites during the course of termination or study suspension.

## **11.9 Safety Oversight**

Subject safety will be monitored through collection of SAEs.

## **11.10 Quality Assurance and Quality Control**

The Investigator-Sponsor will verify that the clinical trial is conducted, and data are documented (recorded), and reported in compliance with the protocol, ICH GCP, and applicable regulatory requirements (e.g., Good Laboratory Practices [GLP], Good Manufacturing Practices [GMP]).

Each clinical site will perform ongoing internal quality management review of their study conduct, data documentation and completion. The investigational site will provide direct access to all trial related sites, source data/documents, and reports for the purpose of monitoring and auditing by the Investigator-Sponsor, and inspection by local and regulatory authorities.

### **11.10.1 Clinical Monitoring**

During study conduct, the Investigator-Sponsor or its agent will conduct periodic on-site or remote monitoring visits to ensure that the protocol and GCP are being followed. The Investigator-Sponsor or designee will review source documents to confirm that the data recorded on the eCRFs is accurate. The Investigator/institution will allow the Investigator-Sponsor's monitors or designees and appropriate regulatory authorities direct access to source documents to perform this verification.

The study site may also be subject to Quality Assurance audits performed by the Investigator-Sponsor or companies working with or on behalf of the Investigator-Sponsor, and/or review by the IRB, and/or to inspection by appropriate regulatory authorities.

It is important that the Investigator(s) and their relevant personnel are available during the monitoring visits and possible audits or inspections and that sufficient time is devoted to the process.

### **11.10.2 Protocol Deviations**

A protocol deviation is generally an unplanned excursion from the protocol that is not implemented or intended as a systematic change. The Investigator is responsible for ensuring the study is conducted in accordance with the procedures and evaluations described in this protocol and must protect the rights, safety, and welfare of subjects. The Investigator should not implement any deviation from, or changes of, the protocol, unless it is necessary to eliminate an immediate hazard to trial subjects.

A protocol waiver is a documented prospective approval of a request from an Investigator to deviate from the protocol.

For the purposes of this protocol, deviations requiring notification to the Investigator-Sponsor are defined as any subject who:

- Entered into the study even though they did not satisfy entry criteria
- Received wrong treatment or incorrect dose
- Received excluded concomitant treatment, including commercial Auryxia
- Does not discontinue prescribed phosphate-lowering therapy or oral/IV iron therapy in response to low phosphorus or elevated iron indices, per Section 7.1.2.1
- Does not receive quarterly monitoring of serum phosphorus and iron indices (with documented Investigator review).

When one of these deviations from the protocol is identified for an individual subject, the Investigator or designee must ensure the Investigator-Sponsor is notified. If the Investigator determines that the deviation impacts the safety of a subject, the Investigator must contact the Investigator-Sponsor immediately. The Investigator-Sponsor will follow-up with the Investigator, as applicable, to assess the deviation and the possible impact to the safety and/or efficacy of the subject to determine subject continuation in the study.

The Investigator will also assure that deviations meeting IRB/IEC and applicable regulatory authorities' criteria are documented and communicated appropriately. All documentation and communications to the IRB/IEC and applicable regulatory authorities will be filed in the Investigator Site Files and will be provided to the Investigator-Sponsor and maintained within the Trial Master File.

Note: Other deviations outside of the categories defined above, that are required to be reported by the IRB/IEC in accordance with local requirements, will be reported, as applicable.

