Iron accumulation is a potential risk of long-term treatment with ferric citrate or other iron-containing medicinal products. Continued excessive iron uptake can lead to iron deposition in body tissues and ultimately to organ damage. To prevent excessive iron accumulation, laboratory iron measures will be monitored regularly, and the ferric citrate, oral or IV iron dose will be adjusted in response to sustained elevations of TSAT.

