### **3.3.2 Known Potential Benefits**

The ability of ferric citrate to lower serum phosphorus in adult patients with CKD on dialysis was demonstrated in Study KRX-0502-304. In that pivotal study, the efficacy of ferric citrate for controlling serum phosphorus levels was similar to that of calcium acetate and/or sevelamer carbonate, and better than that of placebo.

Study KRX-0502-204 was a 12-week, double-blind, placebo-controlled study.

Study KRX-0502-306 was a 24-week study consisting of a 16-week, randomized, double-blind, placebo-controlled, efficacy period followed by an 8-week, open-label, safety extension period in which all subjects remaining in the study, including those in the placebo group, received ferric citrate. Both studies showed reduction in serum phosphorus levels with ferric citrate treatment compared with placebo. In addition, the efficacy of ferric citrate for the treatment of IDA was demonstrated in 2 controlled studies in adult subjects with CKD not on dialysis.

Ferric citrate's potential benefits are supported by its approval for use in the US for the control of serum phosphorus levels in adult patients with CKD on dialysis, and for the treatment of IDA in adult patients with CKD not on dialysis.

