### **7.5.4 Prohibited Medications/Procedures**

Potentially eligible subjects may or may not be receiving phosphate-lowering or iron-repletion therapy prior to Day 1; however, if a subject is receiving commercial ferric citrate (Auryxia), it must be stopped at or prior to Day 1.

Prescription of commercial Auryxia is prohibited for all subjects at any time after Day 1/Baseline in the study. All other therapies may be administered per SOC. Receipt of commercial Auryxia for longer than 4 consecutive weeks during trial participation will be considered a protocol deviation. If the Investigator is unwilling to discontinue commercial Auryxia, study drug should be discontinued, and the subject should continue to be followed per the SoA including the Follow Up Visit (Visit 6).

Since ferric citrate will be administered to 50% of subjects, standard drug-drug interactions reported in the Auryxia package insert approved by the Food and Drug Administration (FDA) in the US shall be followed. [Auryxia USPI 2021].

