#### 3.4.3. Protocol Deviations

Important protocol deviations will be summarized for the full analysis population. For the purposes of this protocol, important deviations are defined as any subject who:

- Entered the study even though they did not satisfy entry criteria
- Received wrong treatment or incorrect dose (i.e., patient not stopping IP when protocol required, patient not decreasing IP when serum phosphorus and iron indices indicate)
- Received excluded concomitant treatment, including commercial Auryxia
- Does not discontinue prescribed phosphate-lowering therapy or oral/IV iron therapy in response to low phosphorus or elevated iron indices, per Section 7.1.2.1
- Does not receive quarterly monitoring of serum phosphorus and iron indices (with documented Investigator review).

A listing of subjects with important protocol deviations will be provided.

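### Protocol 11.10.2 and 8.1.2 let a deviation, or a sponsor or investigator decision, end a randomised subject's study participation, with no endpoint follow-up to Month 9 provided afterwards

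*Protocol*

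**What the plan says.** **Passages that permit removal from the study.** Protocol 11.10.2 names five deviations that must be notified to the sponsor: entry criteria not met, wrong treatment or dose, excluded concomitant treatment (including commercial Auryxia), failure to stop other binders or iron, and missed quarterly monitoring. The fourth reads "Does not discontinue prescribed phosphate-lowering therapy or oral/IV iron therapy in response to low phosphorus or elevated iron indices, per Section 7.1.2.1". For the wrong-dose category, SAP 3.4.3 gives as examples "patient not stopping IP when protocol required, patient not decreasing IP when serum phosphorus and iron indices indicate". After any of the five, the sponsor follows up with the investigator "to assess the deviation and the possible impact to the safety and/or efficacy of the subject to determine subject continuation in the study". Separately, 8.1.2 lets an investigator stop study drug or withdraw the subject from the study. Its reasons include significant non-compliance, TSAT, ferritin or phosphorus values that stay out of range, and sponsor decision.

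**Passages that point the other way.**
- 7.4 rules out withdrawal from the study over study drug compliance.
- 7.5.4 covers a subject whose investigator will not stop commercial Auryxia: "study drug should be discontinued, and the subject should continue to be followed per the SoA including the Follow Up Visit (Visit 6").
- 10.3 states that "Discontinuation from study intervention is different from discontinuation from the study, and remaining study procedures will be completed as indicated by the study protocol", with withdrawn consent as the exception. Both 10.3 and SAP 3.3 say that endpoint data collected on and off drug enter the primary analysis.

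**Follow-up available to a subject who leaves.** Schedule of Activities footnote D gives a virtual visit 30 days after the last dose, covering SAEs and vital status. The endpoint assessment defined in footnote O is marked at that visit. Sections 5.4 and 8.2 add a 30-day vital status check after dialysis or transplant, and 8.3 adds a records search for subjects lost to follow-up. SAP 3.3 caps the vital status date at 37 days after early termination.

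**The concern.** The protocol separates stopping drug from leaving the study, and its analysis relies on that separation. Section 11.10.2 puts the decision on the wrong side of the line: it concerns continuation in the study. A subject removed at Month 3 could start dialysis or die at Month 7 without the event being counted, in an analysis meant to use all endpoint data. The endpoint affected is the one that 9.3 and 10.4.2 call confirmatory, and data that were never collected cannot be recovered by a sensitivity analysis.

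The loss may also differ by arm. Two of the five categories can arise after a low phosphorus or high iron result. On phosphorus, 3.3.2 says of two placebo-controlled studies: "Both studies showed reduction in serum phosphorus levels with ferric citrate treatment compared with placebo". On iron, 3.3.1 says: "Iron accumulation is a potential risk of long-term treatment with ferric citrate or other iron-containing medicinal products". The entry limits in 6.1 (phosphate at least 3.0 mg/dL, TSAT at most 45%, ferritin at most 500 ng/mL) coincide with the limits at which 7.1.2.1 begins to require action, so a subject can enter at the edge. Even a blinded, even-handed rule could therefore remove more subjects from one arm. If their risk differs from that of the subjects who remain, the censoring is informative.

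**Working it through.** **1. The same event under different sections**

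| Event | 11.10.2 or 8.1.2 | Elsewhere |
|---|---|---|
| Commercial Auryxia | Notifiable; continuation in the study to be determined (11.10.2) | Drug stopped if the investigator will not stop Auryxia; followed through Visit 6 (7.5.4) |
| Non-compliance or incorrect dose | Withdrawal from the study allowed (8.1.2); continuation to be determined (11.10.2) | No withdrawal over compliance (7.4) |
| Iron values still high | Withdrawal from the study allowed (8.1.2) | Visits continue whether or not drug is given (7.1.2.1) |
| Drug stopped for any reason | – | Procedures continue unless consent is withdrawn (10.3) |

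No passage carries endpoint assessment to Month 9 for a subject removed under the middle column.

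**2. The plan's own figure (10.1, SAP 3.1)**

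Inputs: control rate 0.94 per person-year, 0.75 years of follow-up each, HR 0.60, 200 per arm, two-sided alpha 0.05.

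- Control event probability: 1 − exp(−0.94 × 0.75) = 0.506.
- Active: 1 − exp(−0.94 × 0.60 × 0.75) = 0.345.
- Expected events: 200 × (0.506 + 0.345) ≈ 170.
- Freedman: 169 events needed, N = 397. Schoenfeld: 162 events, N = 381.
- Power at 170 events: Φ(√170.2 × 0.4/1.6 − 1.96) = 0.903 (Freedman); Φ(½ × √170.2 × |ln 0.60| − 1.96) = 0.915 (Schoenfeld).

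The stated 400 patients for 90% power is reproduced. No allowance for removals is stated.

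**3. Power under removal**

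The documents give no removal rates, so those below are assumptions. A fraction f of an arm is removed at t = 0.25 years. Events per arm = 200 × [(1 − f)(1 − e^(−0.75λ)) + f(1 − e^(−0.25λ))], where λ is the arm's event rate.

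| Removed, active / placebo | Events | Power (Freedman to Schoenfeld) |
|---|---|---|
| 0 / 0 | 170 | 0.903 to 0.915 |
| 5% / 2% | 167 | 0.898 to 0.910 |
| 10% / 5% | 163 | 0.891 to 0.903 |
| 20% / 5% | 159 | 0.883 to 0.896 |

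The largest loss is about 2 points.

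**4. Bias under informative removal**

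Simulated with 400,000 per arm and exponential event times, with the average control rate held at 0.94. Assumptions: a subgroup of 5% or 10% has half or twice the hazard of the rest; all of it is removed at 3 months on active and one fifth of it on placebo.

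| Subgroup | Hazard vs rest | True HR 1.00 estimated at | True HR 0.60 estimated at |
|---|---|---|---|
| 5% | half | 1.02 | 0.61 |
| 5% | twice | 0.99 | 0.59 |
| 10% | half | 1.03 | 0.62 |
| 10% | twice | 0.97 | 0.58 |

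A harsher one-sided case was also run: 15% of active and 3% of placebo removed between Months 3 and 6, all from a subgroup with three times the hazard. It gives a null HR of about 0.96 to 0.97. Where removal was unrelated to risk, the HR stayed at 1.00.

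For scale, SE(log HR) ≈ 2/√170 = 0.153, so a shift from 1.00 to 0.97 or 1.03 is about 0.2 standard errors. Steps 3 and 4 credit no follow-up after removal. If the 30-day check is done, the loss is smaller.

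**The case against.** The strongest reply is that this is loose wording in a quality-assurance section and the rest of the protocol already governs. The clause permits removal but does not require it, and the sponsor acts with the investigator, both blinded. The first part of 8.1.2 asks subjects who stop drug to stay in the study, and cancels endpoint assessment only for those who decline visits and withdraw consent. SAP 3.5 has no separate disposition category for deviations. All of this is correct and limits how often removal is likely. It does not settle which section prevails when a site applies 11.10.2 or the list in 8.1.2 as written.

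Four stronger readings are tempting, and the documents do not support them.
- **That a removed subject gets no further check.** Footnotes D and O give a general 30-day visit with vital status and endpoint assessment, and the SAP's 37-day cap presupposes that vital status is collected. It is mainly later events that are at risk.
- **That more ferric citrate subjects will be removed.** A deviation needs a failure to act on a result, not only a crossed limit. One category also needs other binders or iron to be in use; these are allowed in both arms and could be commoner on placebo. Wrong treatment needs no laboratory trigger. Failing to stop drug when required also covers dialysis, transplant, enzyme elevations and pregnancy.
- **That the bias favours the drug.** Section 3.2.2 links declining kidney function to high phosphorus, and 3.1 links anemia to worse outcomes. Subjects with low phosphorus or high iron could therefore be at lower risk, which would bias against the drug.
- **That 8.2 closes the list of reasons for leaving the study.** Its wording leaves the list open, so the firm conflicts are with 7.4, 7.5.4 and 10.3.

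**Conclusion.** The concern holds as a contradiction between sections and an avoidable gap in endpoint follow-up. Both 11.10.2 and 8.1.2 allow a randomised subject to be taken out of the study for reasons that 7.4, 7.5.4 and 10.3 say should not end follow-up, and dialysis or death after the 30-day check can then be lost. A difference between arms is plausible but is an inference: no deviation or removal rates are given, and the direction of bias is unknown.

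Under the main assumptions the size is small: a null HR estimated at about 0.97 to 1.03, a true 0.60 at about 0.58 to 0.62, and a power loss of at most about 2 points even with 20% of the active arm removed at 3 months. The case for acting is that the correction is nearly free and the missing data could not be recovered later. A claim that the trial's result would be materially biased is not supported.

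**What to change.** Reconcile 11.10.2 and 8.1.2 with 7.4, 7.5.4 and 10.3. Changing 11.10.2 alone would leave the same route open in 8.1.2. In 11.10.2, drop continuation in the study as the object of the decision, and in both sections state:

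*A protocol deviation, or a sponsor or investigator decision, does not by itself end study participation. Every randomised subject is followed for dialysis, death, transplant and hospitalization per the SoA, by visit or through medical records, unless consent is withdrawn or an existing endpoint rule (dialysis, transplant) applies.*

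Decisions on study drug are left as they are. The cost is a short protocol amendment and a little more follow-up effort for the few subjects affected. It adds no visits beyond those already in the SoA and does not change the sample size.
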